9.2 Regulatory Requirements

The Sponsor or designee is responsible for regulatory submissions and reporting to the Investigators of serious adverse events (SAEs) including suspected unexpected serious adverse reactions (SUSARs) per the ICH E6. Country-specific regulatory requirements will be followed in accordance with local country regulations and guidelines.

Institutional Review Boards (IRBs)/Independent Ethics Committees (IECs) will be notified of any SAE according to applicable regulations.

In addition to the Investigator's assessment of relatedness of SAEs to the Study Drug, the Sponsor or designee will evaluate the available information and perform an independent causality assessment of all reported SAEs. While the Sponsor may upgrade an Investigator's decision it is not permissible to downgrade the Investigator's opinion for the purposes of determining whether the SAE meets the definition of a SUSAR.

Appropriate personnel at the Sponsor or designee will unblind SUSARs for the purpose of regulatory reporting. The Sponsor or designee will submit SUSARs to Regulatory Agencies in blinded or unblinded fashion according to local law. The Sponsor or designee will submit SUSARs to Investigators in a blinded fashion.

9.3 Definitions

9.3.1 *Adverse Event*

An adverse event (AE) can be any unfavorable and unintended sign (including an abnormal laboratory finding), symptom, or disease temporally associated with the use of a medicinal (investigational) product, whether or not the AE is considered related to the medicinal (investigational) product.

Adverse events are to be identified between study visits by evaluating components of the medical record that contain valid and verifiable claims about a medically untoward event. For hemodialysis subjects, this includes a complete review of changes in the dialysis prescription in the dialysis chart orders section or information provided to the study staff directly by the subject. Dialysis treatment summaries (rnn-sheets) should be reviewed for pertinent information when indicated.

9.3.2 *Adverse Drug Reaction and Unexpected Adverse Drug Reaction*

All noxious and unintended responses to a medicinal product related to any dose should be considered adverse drug reactions (ADR).

An unexpected ADR is any ADR, the nature or severity of which is not consistent with the applicable product information, e.g., Investigator's Brochure for an unapproved medicinal (investigational) product.

9.3.3 *Serious Adverse Event (SAE)*

A SAE is any AE that in the view of either the Investigator or Sponsor, meets any of the following criteria:

- Results in death
- Is life threatening: that is, poses an immediate risk of death at the time of the event
An AE or suspected adverse reaction is considered "life-threatening" if, in the view of either the Investigator or Sponsor, its occurrence places the subject at immediate risk of death. It does not include an AE or suspected adverse reaction that, had it occurred in a more severe form, might have caused death
- Requires inpatient hospitalization or prolongation of existing hospitalization
Hospitalization is defined as an admission of greater than 24 hours to a medical facility and does not always qualify as an AE
- Results in a persistent or significant incapacity or substantial disruption of the ability to conduct normal life functions

- Results in a congenital anomaly or birth defect in the offspring of the subject (whether the subject is male or female)
- Important medical events that may not result in death, are not life-threatening, or do not require hospitalization may also be considered serious when, based upon appropriate medical judgment, they may jeopardize the subject and may require medical or surgical intervention to prevent one of the outcomes listed in this definition. Examples of such medical events include allergic bronchospasm requiring intensive treatment in an emergency room or at home, blood dyscrasias or convulsions that do not result in inpatient hospitalization, or the development of drug dependency or drug abuse

9.3.4 Adverse Event of Interest

Adverse events of interest (AEoI) includes both serious and non-serious events of MB and CRNMB, defined in [Section 8.5.3](#) (Safety Monitoring for Bleeding Events).

AEoI are required to be reported by the Investigator to the Sponsor immediately, no more than 24 hours of the Investigator's first knowledge of the event.

9.4 Monitoring and Recording Adverse Events

Any pre-existing conditions or signs and/or symptoms present in a subject prior to the start of the study (i.e., before informed consent) should be recorded as Medical History and not recorded as AEs unless the pre-existing condition worsened to an extent not consistent with the natural history of the condition.

In subjects with ESRD requiring dialysis, events due to abnormalities of serum electrolytes such as sodium, potassium, chloride, bicarbonate, calcium, and phosphorus, the anemia of chronic disease, and hypertension are considered part of their underlying condition. In addition, mechanical complications of vascular accesses are common in subjects that require dialysis. Events that are consistent with the natural history of ESRD and the need for dialysis will not be considered AEs unless the course or severity is atypical for this population or thought potentially due to the Study Drug (e.g., due to bleeding) in the opinion of the Investigator. The Investigator should always group signs and symptoms into a single term that constitutes a **single unifying diagnosis** if possible.

9.4.1 Reporting Requirements for Serious Adverse Events Using Electronic Case Report Forms (eCRFs)

In the interest of subject safety, and in order to fulfill regulatory requirements, all SAEs (regardless of their relationship to Study Drug) should be reported to the Sponsor or designee within 24 hours of the Study Center's first knowledge of the event. Similarly, all events that meet the criteria for Major or CRNMB (see definitions in Section 8.5.3) must also be reported within 24 hours of the Study Center's first knowledge of the event.

The collection of SAEs and Clinically-Relevant Bleeding events will begin after the subject signs the informed consent form and stops at the end of the subject's follow-up period which is defined as the last protocol specified Post-Treatment Evaluation Period visit. A SAE should be reported using the electronic SAE submission form whenever possible. In situations where the

electronic SAE submission is unavailable and the Investigator is reporting by telephone, it is important to speak to someone in person vs. leaving a message.

For events that occur prior to Study Drng initiation, the Serious Adverse Event Reporting Form provided to Investigators should be completed and submitted to Ionis or its designee immediately (i.e., no more than 24 hours after learning of the event), either by faxing (using the fax cover sheet provided to Investigators with country-specific fax numbers) or by scanning and emailing the form to [REDACTED]

For events that occur after Study Drng initiation, Investigators should record all case details that can be gathered immediately (i.e., within 24 hours after learning of the event) on the Adverse Event eCRF and submit the report via the electronic data capture (EDC) system. A report should be automatically generated and sent to Ionis or designee by the EDC system.

In the event that the EDC system is unavailable, the **Serious Adverse Event Reporting Form** provided to Investigators should be completed and submitted to Ionis or its designee immediately (i.e., no more than 24 hours after learning of the event), either by faxing (using the fax cover sheet provided to Investigators with country-specific fax numbers) or by scanning and emailing the form to [REDACTED]

Once the EDC system is available, all

information will need to be entered and submitted via the EDC system.

Detailed information should be actively sought and included on Follow-Up Serious Adverse Event Forms as soon as additional information becomes available. All SAEs will be followed until resolution. SAEs that remain ongoing past the subject's last protocol specified Post-Treatment Evaluation visit will be evaluated by the Investigator and Sponsor. If the Investigator and Sponsor agree that the subject's condition is unlikely to resolve, the Investigator and Sponsor will determine the follow-up requirement.

9.4.2 *Non-Serious Adverse Events*

The recording of non-serious AEs will begin after the subject signs the informed consent form and will stop at the end of the subject's follow-up period, which is defined as the last protocol specified Post-Treatment Evaluation Period visit. The Investigator will monitor each subject closely and record all observed or volunteered AEs on the Adverse Event Case Report Form.

9.4.3 *Evaluation of Adverse Events (Serious and Non-Serious)*

The Investigator's opinion of the following should be documented on the Adverse Event Case Report Form.

9.4.3.1 ***Relationship to the Study Drug***

The event's relationship to the Study Drng (ISIS 416858 or placebo) is characterized by one of the following:

- **Related:** There is clear evidence that the event is related to the use of Study Drng, e.g., confirmation by positive re-challenge test
- **Possible:** The event cannot be explained by the subject's medical condition, concomitant therapy, or other causes, and there is a plausible temporal relationship between the event and Study Drng (ISIS 416858 or placebo) administration
- **Unlikely/Remote:** An event for which an alternative explanation is more likely (e.g., concomitant medications or ongoing medical conditions) or the temporal relationship to Study Drng (ISIS 416858 or placebo) administration and/or exposure suggests that a causal relationship is unlikely (For reporting purposes, Unlikely/Remote will be grouped together with Not Related)
- **Not Related:** The event can be readily explained by the subject's underlying medical condition, concomitant therapy, or other causes, and therefore, the Investigator believes no relationship exists between the event and Study Drng (ISIS 416858 or placebo)

9.4.3.2 ***Severity***

The severity of AEs and SAEs will be graded based on criteria from the Common Terminology Criteria for Adverse Events (CTCAE) Version 4.03, June 2010 (refer to [Appendix D](#)). Any AE not listed in Appendix D will be graded as follows:

- **Mild:** The event is easily tolerated by the subject and does not affect the subject's usual daily activities
- **Moderate:** The event causes the subject more discomfort and interferes with the subject's usual daily activities
- **Severe:** The event is incapacitating and causes considerable interference with the subject's usual daily activities

If the event is a SAE, then **all** applicable seriousness criteria must be indicated (criteria listed in [Section 9.3.3](#)).

9.4.3.3 ***Action Taken with Study Drug***

Action taken with Study Drng (ISIS 416858 or placebo) due to the event is characterized by one of the following.

- **None:** No changes were made to Study Drng (ISIS 416858 or placebo) administration and dose
- **Permanently Discontinued:** Study Drng was discontinued and not restarted
- **Temporarily Interrupted, Restarted- Same Dose:** Dosing was temporarily interrupted or delayed due to the AE and restarted at the same dose

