2.3.8 Concomitant Medications

Concomitant medications will be coded using WHO Drug dictionary Version Mar 2018 and summarized by ATC class, generic name and treatment group. Prior medications and Concomitant medications will be summarized by treatment group for the Safety population. Prior medications include medications started and stopped prior to study drug administration (Day 1). Concomitant medications include medications (1) started prior to, and continued after Day 1, or (2) medications started on or after Day 1.

All transfusions will be summarized and listed for all patients as recorded on the transfusion logCRF.

2.3.9 *Ancillary procedures*

Ancillary procedures will be provided in the listing.

2.3.10 *Changes in Dialysis Access*

Changes in dialysis access prescription will be listed.

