1.2 Exploratory Objectives

To evaluate the incidence of myocardial infarction (MI), stroke, systemic embolism, and cardiovascular mortality.

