2.2 Therapeutic Rationale

Approximately 2 million individuals receive dialysis for end-stage renal disease (ESRD) globally and this number is increasing rapidly as both the incidence of ESRD rises and access to dialysis as a life sustaining therapy increases (Caskey et al. 2011). Dialysis patients are at high risk of thrombotic events due to their high degree of comorbid conditions and because they have a hypercoagulable state. This hypercoagulable state appears to be driven by widely used drugs (e.g., erythropoiesis stimulating agents), inflammation and endothelial dysfunction from uremia, and contact between blood and the extracorporeal circuit. The hypercoagulable state results in clinically meaningful negative outcomes. The risk of stroke in dialysis patients may be 10-times higher than the general population (Sood et al. 2009). Dialysis patients have a 5-fold higher risk of myocardial infarction than the general population and even moderate chronic kidney disease alone is considered the risk equivalent of diabetes mellitus for cardiovascular thrombotic events (Go et al. 2004; Tonelli et al. 2012). Furthermore, dialysis patients depend on patent vascular access to receive hemodialysis. Dialysis patients have a high chance, approximately 10% chance per year of having their vascular access compromised by thrombosis resulting in a potentially life-threatening situation requiring urgent intervention (Jean-Baptiste et al. 2008; Schild et al. 2008). Finally, dialysis patients are hospitalized an average of 3 times per year and are at high risk of VTE (Tveit et al. 2002). Despite this high risk of VTE, there remains considerable uncertainty as to the benefit-to-risk ratio of VTE prophylaxis. This is of particular importance when considering the optimal treatment for ESRD, renal transplantation, in which VTE can compromise the ability to receive a transplant, the function of an already transplanted kidney,

and/or the life expectancy of a patient who recently received a transplant (i.e., post-operative VTE) (Irish 2004).

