In summary, while the number of patients with chronic renal disease on hemodialysis keeps growing, anticoagulation treatment options to prevent the sequelae of ESRD remain limited. Traditional therapies such as warfarin and aspirin have limited efficacy, perhaps in part due to the mechanisms for thrombosis in ESRD, and expose patients to undue bleeding risk. Therefore, a therapy like ISIS 416858 that is being developed to provide anticoagulation without increased risk of bleeding could effectively reduce thrombosis which may positively affect the morbidity and mortality in these high-risk patients. Initial data demonstrating that treatment with ISIS 416858 for 12 weeks reduced FXI activity levels up to 80% without any increase in clinically-relevant non-major or major bleeding support this notion. The development of ISIS 416858 will ultimately determine whether the need for heparin during the dialysis procedure could be reduced or eliminated which could reduce the risk of major hemorrhage and improve the dialysis procedure. This concept is supported by a report in the literature of a dialysis patient with severe congenital FXI deficiency (less than 3% of normal) who received hemodialysis for several months without heparin or any other anticoagulant and did not exhibit clotting in the extracorporeal circuit or any bleeding complications (Takamizawa et al. 2014). Results from an initial study in 43 ESRD subjects on hemodialysis (ISIS 416858-CS4) indicated that ISIS 416858 significantly reduced the incidence of severe clotting events in the dialyzer circuit at doses of 200 mg and 300 mg per week without increased major or Clinically-Relevant Non-Major Bleeding (CRNMB), providing further support to this finding.

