8.5.3 Safety Monitoring for Bleeding Events

Subjects will be evaluated for occurrence of bleeding events continuously after the start of Study Drug treatment (Day 1) up to Day 260 for all cohorts. All bleeding events are considered AEs and reported on adverse event case report form.

Bleeding events that are either major or CRNMB (as defined below) will need to be monitored and treated immediately. Subjects with a suspected bleeding event will undergo additional testing if deemed appropriate by the treating physician and an (S)AE case report form will be completed. In addition, if bleeding is considered significant, Hb, HCT, aPTT, PT, INR, FXI activity and antigen, and platelet count are to be obtained. In addition, approximately 2 mL of

K2EDTA anticoagulated blood will be collected and resulting plasma must be stored allowing for a centralized assessment of ISIS 416858 concentrations.

In addition, if a minor bleeding event occurs, the Investigator should notify the Sponsor Medical Monitor (or designee) and additional testing of coagulation parameters (aPTT, PT, INR), platelet count, and platelet volume may be performed.

Definitions:

Major bleeding (MB) is defined as one of the following:

1. Fatal bleeding
2. Symptomatic bleeding in a critical area or organ, such as intracranial, intraspinal, intraocular, retroperitoneal, intraarticular if in a major joint, or pericardial, or intramuscular with compartment syndrome
3. Clinically overt bleeding leading to transfusion of 2 units of packed red blood cells or whole blood or a fall in Hb of 20 g/L (1.24 mmol/L) or more within 24 hours

Clinically-Relevant Non-Major Bleeding (CRNMB) is defined as overt bleeding not meeting the criteria for MB but that resulted, for example, in medical examination, intervention, or had clinical consequences for a subject (Biller et al. 2007).

Minor bleeding events are those that do not fulfill the criteria for MB or CRNMB events (defined above), for example excess bruising, petechiae, gingival bleeding on brushing teeth.

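### Protocol 9.4 lets sites leave dialysis-typical events off the AE form, which conflicts with 8.5.3 for minor access-site bleeding and leaves routine vascular-access thrombosis without assured capture

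*Combined protocol and SAP*

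**What the plan says.** Protocol 9.4 lists conditions regarded as part of ESRD and adds that "mechanical complications of vascular accesses are common in subjects that require dialysis". It then gives the rule: "Events that are consistent with the natural history of ESRD and the need for dialysis will not be considered AEs unless the course or severity". The same sentence goes on to except an event that "is atypical for this population or thought potentially due to the Study Drug (e.g., due to bleeding) in the opinion of the Investigator". So the exclusion is conditional, and the investigator's opinion decides.

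Protocol 8.5.3 has no such condition: "All bleeding events are considered AEs and reported on adverse event case report form". Sections 9.3.4 and 9.4.1 separately require every MB and CRNMB to be reported within 24 hours, without reference to cause. The primary safety outcome is MB plus CRNMB during treatment. SAP 2.3.3.3 also tabulates minor bleeding by treatment group.

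On access thrombosis, protocol 2.2 says that dialysis patients have an "approximately 10% chance per year of having their vascular access compromised by thrombosis", and that the drug "could effectively reduce thrombosis which may positively affect the morbidity and mortality in these high-risk patients". The exploratory objective is "To evaluate the incidence of myocardial infarction (MI), stroke, systemic embolism, and cardiovascular mortality". SAP 2.3.3.4 adds three CRF-based categories of interest: cerebrovascular accident or TIA, coronary ischemia, and venous thromboembolism. For access itself, SAP 2.3.10 says "Changes in dialysis access prescription will be listed". SAP 2.3.9 and 2.6 likewise only list ancillary procedures and changes in dialysis prescription.

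**The concern.** Two kinds of event meet the 9.4 filter.

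The first is bleeding at the access site. If a site regards it as usual for dialysis and not drug-related, 9.4 says it is not an AE, while 8.5.3 says it is. Which events are counted then depends on the section the site follows and on an opinion about cause. In a safety study of an antithrombotic drug, bleeding should be counted before anyone judges its cause.

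The second is a clotted fistula, graft or catheter. It is common in this population, and an investigator is unlikely to attribute it to an antithrombotic drug. Under 9.4 a routine case need not be an AE, and no endpoint or named category is sure to pick it up. The synopsis gives the indication as evaluation of antithrombotic effects in hemodialysis patients, so a by-arm count of this event is something a reader of the results would expect.

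**Working it through.** The plan states no figure on this point, so there is none to reproduce. The check is mainly a comparison of sections, followed by an illustration of size.

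**Bleeding: 9.4 against 8.5.3.** Take an ordinary needle-site bleed, typical in course and not suspected to be drug-related.
- Under 9.4 neither exception applies, so it is not an AE. The bleeding example in that sentence illustrates suspected drug causation. It does not exempt bleeding as such.
- Under 8.5.3 it is an AE and goes on the AE form.
- If it is recognised as MB or CRNMB, 9.3.4 and 9.4.1 require it anyway.

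The conflict therefore affects minor bleeds. It also affects borderline ones: CRNMB includes overt bleeding that led to examination or intervention, and a site that sees an access bleed as routine may never ask whether it qualifies.

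On direction, suppose a patient with such a bleed is recorded with the same probability f in both arms. The observed difference is then f × (p1 − p0), which is smaller than the true p1 − p0 whenever f < 1. The ratio p1/p0 is unchanged. The documents give no value for f.

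**Access thrombosis: the route to a table.**
1. Is it atypical? Not readily, at about 10% per year (2.2).
2. Is it thought to be drug-related? Under 9.4.3.1 a possible relationship requires that the medical condition does not explain the event. In a dialysis patient it usually does.
3. If it is not an AE, it cannot be an SAE, because 9.3.3 defines SAEs as a subset of AEs.
4. Is it caught elsewhere? It is not named in the exploratory outcomes or in SAP 2.3.3.4. Whether the venous thromboembolism category includes it is not stated. Access changes and ancillary procedures are listed, not summarised.

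**Illustrative size.** Inputs: 204 patients (protocol 3.3), so 204/3 = 68 per cohort. At 3:1 this is 51 active and 17 placebo per cohort, giving 153 active and 3 × 17 = 51 pooled placebo. The rate is 10% per year (2.2). Full follow-up and no drug effect are assumed. The proportion with an event by time t (years) is p = 1 − (1 − 0.10)^t.
- 26 weeks: t = 182/365.25, p = 0.0511. 204 × p = 10.4 patients (active 7.8, placebo 2.6).
- Day 260: t = 260/365.25, p = 0.0723. 204 × p = 14.7 patients (active 11.1, placebo 3.7).
- Simple proportion gives nearly the same: 0.10 × 182/365.25 × 204 = 10.2, and 0.10 × 260/365.25 × 204 = 14.5.
- Over an assumed 5% to 20% per year: 5.1 to 21.5 patients at 26 weeks, and 7.3 to 30.0 by Day 260.

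**Would full capture allow a comparison?** Detecting a halving of p = 0.0511 over 26 weeks (normal approximation, two-sided 5%) has power of about 10% for one dose against placebo (51 v 51) and about 18% for pooled active against placebo (153 v 51). It would not.

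**The case against.** The strongest reply is that the plan protects the events that matter most. MB and CRNMB are reportable whatever their cause (9.3.4, 9.4.1). Sites check for bleeding at every contact, as an item separate from AEs (6.1.3, 6.1.4). An AE or SAE form is completed for a suspected bleed (6.2.2, 8.5.3), and SAP 2.3.3.3 refers to a Bleeding CRF. This stands. A reader might infer that 9.4 makes the primary safety outcome depend on a causality opinion. The documents do not support that for any bleed recognised as MB or CRNMB.

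A reader might also infer that 9.4 removes access thrombosis from the data. It does not. The exclusion is conditional, and the text speaks of mechanical complications without naming thrombosis. Section 2.2 treats the event as potentially life-threatening, so an investigator could judge a given case atypical in severity. Section 9.3.1 has sites review dialysis prescription changes to find AEs, and 6.1.3 allows extra information on thrombotic events. Any case that is recorded appears by treatment group in the TEAE tables, including those for ESRD/procedure-related events (SAP 2.3.3). It would be wrong to say that none can reach a by-arm table.

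Nor is access thrombosis a target event of the trial. Section 2.2 cites it as disease burden, no objective names it, and the planned dialysis-specific measure is clotting of the filter and circuit. Adding a table for it is therefore partly a design suggestion.

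None of this removes the literal conflict between 9.4 and 8.5.3. Nor does it give access thrombosis an assured route into the AE data: extra information on thrombotic events is optional, and chart review finds events that 9.4 then allows the site to leave out.

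**Conclusion.** The point holds within limits. Sections 9.4 and 8.5.3 give different instructions for the same access-site bleed. The practical exposure is minor bleeding, plus borderline bleeds never put forward as CRNMB. Separately, routine access thrombosis can go unrecorded as an AE, and hence as an SAE, leaving only listings.

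The number of access bleeds lost cannot be derived from the documents. About 10 patients with access thrombosis at 26 weeks and about 15 by Day 260 are the events at stake, not the events lost. Those figures also apply one background rate to every access type. What is weakened is the completeness of descriptive by-arm counts. That still matters here, because the sample size has no statistical rationale and most results will be read descriptively.

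**What to change.** Reconcile 9.4 with 8.5.3 by adding one sentence to 9.4, by amendment or site clarification: the natural-history exclusion does not apply to any bleeding event or to any thrombotic event, including vascular-access thrombosis, and these are recorded as AEs regardless of expected course or opinion on cause.

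In the SAP, name vascular-access thrombosis in 2.3.3.4 and 2.5. Tabulate patients with at least one event by treatment group, using the AE, ancillary-procedure and access-change records already collected. Write the rule for identifying a case from those records before unblinding.

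The cost is somewhat more AE entries at sites and one extra table.
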